11.2.4. Analysis of Safety

Safety measures will include the following assessments:

- Demographics\Medical History
- Adverse events and SAEs
- Vital Signs
- Physical Examination
- Clinical laboratory
- ECGs
- Urine pregnancy tests.

Adverse events and medical histories will be coded using the most current version of the Medical Dictionary for Regulatory Activities (MedDRA). New or worsening adverse events after dosing of study drug will be summarized by system organ class, preferred term, and treatment. Lists of subjects who have an SAE or who discontinue from the study due to an adverse event will be provided.

Summary statistics for laboratory values will be provided at baseline, post-baseline visits, and for changes from baseline to post-baseline by treatment. Vital signs parameters will be summarized similarly. Occurrence of significant laboratory abnormalities will be summarized by treatment. Physical examination and urine pregnancy tests data will be summarized and listed.

11.3. Interim Analysis

An interim analysis will be conducted by an independent data monitoring committee (DMC) after approximately 40 subjects have completed the study. Details regarding the conduct of the interim analyses will be specified in a separate document outside of this protocol (e.g. DMC charter). After each meeting, the DMC will advise whether any changes to the sample size or conduct of the study are necessary based on review of unblinded safety and efficacy data.

11.4. Sample Size Calculation

Suppose the percentage of subjects with $\geq 40\%$ reduction in BSA of EBS lesions at Week 16 are 60% and 30%, in Diacerein 1% Ointment or Control Ointment, respectively. Based on a two-

sided, two-sample parallel design for large sample test of proportions with a power of 80% and significance level of 0.05⁷, the sample size needed for a fixed sample size design without interim analysis and sample reconsideration is:

$$n_1 = n_2 = \frac{(z_{\alpha/2} + z_{\beta})^2 (p_1(1-p_1) + p_2(1-p_2))}{(p_2 - p_1)^2} = \frac{(1.96 + 0.84)^2 (0.6 \times (1-0.6) + 0.3 \times (1-0.3))}{(0.6 - 0.3)^2} \approx 39.$$

One interim analysis is planned and sample size will be reconsidered then. We employ O'Brien and Fleming's method⁷, and the sample size is inflated to:

$$n'_1 = n'_2 = n_1 R_B(2, 0.05, 0.2) = 39 \times 1.008 \approx 40,$$

in which $R_B(2, 0.05, 0.2) = 1.008$ is the O'Brien and Fleming's method constant for two-sided test with $\alpha = 0.05$ and $power = 1 - 0.2 = 0.8$.

Thus, at the interim analysis, the sample size per treatment group is $40/2 = 20$. The conditional power will be calculated at the interim analysis, based on which the sample size will be recalculated.

12. DIRECT ACCESS TO SOURCE DATA/DOCUMENTS

12.1. Study Monitoring

Before an investigational site can enter a patient into the study, a representative of Castle Creek Pharmaceuticals, LLC will visit the investigational study site to:

- Determine the adequacy of the facilities
- Discuss with the investigator(s) and other personnel their responsibilities with regard to protocol adherence, and the responsibilities of Castle Creek Pharmaceuticals, LLC or its representatives. This will be documented in a Clinical Study Agreement between Castle Creek Pharmaceuticals, LLC and the investigator.

During the study, a monitor from Castle Creek Pharmaceuticals, LLC or representative will have regular contacts with the investigational site, for the following:

- Provide information and support to the investigator(s)
- Confirm that facilities remain acceptable
- Confirm that the investigational team is adhering to the protocol, that data is being accurately recorded in the case report forms, and that investigational product accountability checks are being performed
- Perform source data verification. This includes a comparison of the data in the case report forms with the patient's medical records at the hospital or practice,

and other records relevant to the study. This will require access to all records for each patient (*e.g.*, clinic charts).

- Record and report any protocol deviations not previously sent to Castle Creek Pharmaceuticals, LLC.
- Confirm AEs and SAEs have been properly documented on eCRFs and confirm any SAEs have been forwarded to Castle Creek Pharmaceuticals, LLC, and their representatives and confirm those SAEs that met criteria for reporting have been forwarded to the IRB/EC, as applicable.

The monitor will be available between visits if the investigator(s) or other staff needs information or advice.

12.2. Audits and Inspections

Authorized representatives of Castle Creek Pharmaceuticals, LLC, a regulatory authority, an Independent Ethics Committee or an Institutional Review Board may visit the site to perform audits or inspections, including source data verification. The purpose of a Castle Creek Pharmaceuticals, LLC audit or inspection is to systematically and independently examine all study-related activities and documents to determine whether these activities were conducted, and data were recorded, analyzed, and accurately reported according to the protocol, Good Clinical Practice guidelines of the International Conference on Harmonization, and any applicable regulatory requirements. The investigator should contact Castle Creek Pharmaceuticals immediately if contacted by a regulatory agency about an inspection.

12.3. Institutional Review Board (IRB) and Ethic Committee (EC)

The Principal Investigator must obtain IRB approval for the investigation. Initial IRB approval, and all materials approved by the IRB for this study including the patient consent form and recruitment materials must be maintained by the Investigator and made available for inspection.

12.4. Data Monitoring Committee

An interim analysis will be conducted by an independent data monitoring committee (DMC) after approximately 40 subjects have completed the study. Details regarding the conduct of the interim analyses will be specified in a separate document outside of this protocol (*e.g.* DMC charter). After each meeting, the DMC will advise whether any changes to the sample size or conduct of the study are necessary based on review of unblinded safety and efficacy data.

13. ETHICS

13.1. Ethics Review

The final study protocol, including the final version of the Informed Consent Form, must be approved or given a favorable opinion in writing by an IRB or IEC as appropriate. The investigator must submit written approval to Castle Creek Pharmaceuticals, LLC before he or she can enroll any patient/subject into the study.

The Principal Investigator is responsible for informing the IRB or IEC of any amendment to the protocol in accordance with local requirements. In addition, the IRB or IEC must approve all advertising used to recruit subjects for the study. The protocol must be re-approved by the IRB or IEC upon receipt of amendments and annually, as local regulations require.

The Principal Investigator is also responsible for providing the IRB with reports of any reportable serious adverse drug reactions from any other study conducted with the investigational product. Castle Creek Pharmaceuticals, LLC will provide this information to the Principal Investigator.

Progress reports and notifications of serious adverse drug reactions will be provided to the IRB or IEC according to local regulations and guidelines.

13.2. Ethical Conduct of the Study

The study will be performed in accordance with ethical principles that have their origin in the Declaration of Helsinki and are consistent with ICH/Good Clinical Practice, applicable regulatory requirements and the Castle Creek Pharmaceutical's policy on Bioethics.

13.3. Written Informed Consent/Assent

The investigator at each investigational center will ensure that written informed consent forms that provide information about the study will be given to adult subjects. For child/adolescent subjects, written informed consent and assent forms will be given to the caregiver and to the applicable subject, respectively. Informed consent forms will contain all the elements required by the ICH E6 Guideline for GCP and any additional elements required by local regulations. The information provided in the informed consent will be in a language understandable to the adult subjects or caregiver of child/adolescent subjects.

The investigator will provide the subject and/or caregiver sufficient time to consider whether to participate in the trial. The investigator will explain to the subject/caregiver that trial participation is voluntary and withdrawal from the study is allowed at any time and withdrawal will not adversely affect the subject's medical care.

At the first study visit, prior to the initiation of any study related procedures, subjects/caregivers will be asked to give written informed consent, and child/adolescent subjects will be asked to give assent, after having been informed of the nature of the study, study procedures and restrictions and risks and benefits. The informed consent and assent documents, as applicable, must be signed and dated by the subject/caregiver prior to study participation. Copies of the signed informed consent and assent documents must be given to the subject/caregiver.

The US FDA does not define the required elements of an assent; however, they must be accurate, not be coercive and must incorporate age appropriate wording. The assent must have a date and signature line for the child. Use of an assent is not a substitute for parental permission. Parents/guardians (caregivers) must be given an IRB/EC approved ICF to review, sign and date.

14. DATA HANDLING AND RECORD KEEPING

14.1. Electronic Case Report Forms

Adequate and accurate case records will be maintained and all relevant observations and data related to the study will be recorded. This will include medical history/physical examination, hematology, clinical chemistry and serology results, inclusion and exclusion criteria, drug administration, and a record of sample collection, hemodynamic measurements, clinical assessments, AEs, and final evaluation as appropriate.

Electronic eCRFs and subject diaries will be used in this study. The eCRF will be electronically signed and dated by the Principal Investigator or his designee after his/her review. After the completion of the study, completed eCRFs will be retained in the archives.

Completed eCRFs will be reviewed by the study monitor in the electronic data capture system against the source documentation for accuracy and completeness.

14.2. Inspection of Records

Castle Creek Pharmaceuticals, LLC will be allowed to conduct site visits to the investigation facilities for the purpose of monitoring any aspect of the study. The Investigator agrees to allow the monitor to inspect the drug storage area, study drug stocks, drug accountability records, subject charts and study source documents, and other records relative to study conduct.

14.3. Retention of Records

The Principal Investigator must maintain all documentation relating to the study for a period of 2 years after the last marketing application approval, or if not approved 2 years following the discontinuance of the test article for investigation. If it becomes necessary for Castle Creek Pharmaceuticals, LLC or the Regulatory Authority to review

any documentation relating to the study, the Investigator must permit access to such records.

15. PUBLICATION POLICY

The investigator is obliged to provide the sponsor with complete test results and all data derived by the investigator from the study. During the study, only the Sponsor may make study information available to other study investigators or to regulatory agencies, except as required by law or regulation. Except as otherwise allowable in the clinical study site agreement, any public disclosure (including publicly accessible websites) related to the protocol or study results, other than study recruitment materials and/or advertisements, is the sole responsibility of the Sponsor.

The Sponsor may publish any data and information from the study (including data and information generated by the investigator) without the consent of the investigator. Manuscript authorship for any peer-reviewed publication will appropriately reflect contributions to the production and review of the document. All publications and presentations must be prepared in accordance with this section and the Clinical Study Site Agreement. In the event of any discrepancy between the protocol and the Clinical Study Site Agreement, the Clinical Study Site Agreement will prevail.

If the study is being conducted as part of a multicenter clinical study, data from all sites participating in the study will be pooled and analyzed by the Sponsor or the Sponsor's designee. The first publication of the study results shall be made in conjunction with the results from other study sites as a multicenter publication. If a multicenter publication is not forthcoming within 24 months of completion of the study at all sites, the investigator may publish or present the results generated at his or her site.

The investigator will provide the Sponsor with a copy of any proposed publication or presentation for review and comment at least 60 days prior to such presentation or submission for publication. The Sponsor shall inform the investigator in writing of any changes or deletions in such presentation or publication required to protect the Sponsor's confidential and proprietary technical information and to address inaccurate data or inappropriate interpretations in the context of any pooled multicenter results. At the expiration of such 60-day period, the investigator may proceed with the presentation or submission for publication unless the Sponsor has notified the institution or the investigator in writing that such proposed publication or presentation discloses the Sponsor's confidential and proprietary technical information. Further, upon the request of the Sponsor, the investigator will delay the publication or presentation for an additional 90 days to permit the Sponsor to take necessary actions to protect its intellectual property interests.

1. INTRODUCTION

The purpose of this document is to provide a description of the statistical methods and procedures to be implemented for the analysis of data from protocol number CCP-020-301 (DELIVERS trial). During the conduct of the DELIVERS trial, the Sponsor, Investigators, and all currently blinded teams at Medpace will remain blinded until completion of the trial. This document is based on the Global Protocol Amendment 3a document. If circumstances arise during the study such that more appropriate analytic procedures become available, the statistical analysis plan (SAP) may be revised. Any revisions to the SAP (both alternative and additional methods) will be made prior to database lock. Reasons for such revisions will be described in the final Clinical Study Report (CSR).

2. OVERVIEW

2.1. Objectives

The primary objective of the study is to compare the efficacy of Diacerein 1% Ointment to Control Ointment when applied once-daily for 8 weeks in subjects with epidermolysis bullosa simplex (EBS).

The secondary objectives are to compare the effects of Diacerein 1% Ointment to Control Ointment in subjects with EBS in:

- Pain
- Pruritus
- Safety and tolerability

2.2. Trial Design

This is an international, multicenter, randomized, double-blind, vehicle-controlled, parallel group study to evaluate the safety and efficacy of topical Diacerein 1% Ointment for the treatment of subjects with EBS. Subjects at least 4 years of age with a genetic confirmation of EBS (based on either existing documentation or results from a sample collected as part of the study) who meet all the inclusion criteria and none of the exclusion criteria at Visit 1 will be eligible for enrollment in the study.

Eligible subjects will be randomized in a 1:1 ratio to either receive 8 weeks of once-daily application of Diacerein 1% Ointment or Control Ointment to all EBS lesions. Approximately 80 subjects will be randomized at approximately 22 international investigational centers. The randomization will be stratified by genotype (KRT5 and/or KRT14 versus other genotypes) and age group (<8 and ≥8 years old). Subjects/caregivers will apply the assigned study medication to all EBS lesions, including any new EBS lesions that develop, once daily, every evening during the 8-week treatment period. No study medication applications will be made to any lesion that becomes infected until the infection resolves with appropriate investigational center specific medical care.

Subjects/caregivers will be instructed on the use of the electronic diary (eDiary) to record patient reported outcomes of pruritus, pain and mobility and to document bandage use, blister lancing compliance, new lesions that develop in between study visits, routine cleanser use and study medication applications. Adverse events, clinical laboratory data, pharmacokinetic (PK) sampling, efficacy evaluations and determination of study medication use will be routinely collected.

The duration of study participation is anticipated to be a maximum of 158 days per subject (~22 weeks). This includes the up to 6-week screening period, an 8-week treatment period and an 8-week no-treatment follow-up period.

Study visits are summarized as follows:

- Visit 1 (Week -6/Day -42 to 0) enrollment, start randomization eligibility assessment period
- Visit 2 (Week 0/Day 1) randomization; first study medication application
- Visit 3 (Week 1/Day 8) treatment period follow-up
- Visit 4 (Week 4/Day 29) treatment period follow-up
- Visit 5 (Week 6/Day 43) treatment period follow-up
- Visit 6 (Week 8/Day 57) end of the treatment period
- Visit 7 (Week 12/Day 85) no treatment follow-up
- Visit 8 (Week 16/Day 113) no treatment follow-up, end of study

A detailed schedule of procedures is provided in [Table 1](#).

3. STUDY ENDPOINTS

3.1. Efficacy Variables

3.1.1. Primary Endpoint

The proportion of subjects who achieve $\geq 60\%$ reduction in BSA of EBS lesions within the Assessment Area from Baseline to Visit 6 (Week 8).

3.1.2. Key Secondary Endpoint

The proportion of subjects achieving success on the IGA of the Assessment Area, where success is defined as at least a 2-point reduction, from Baseline to Visit 6 (Week 8).

3.1.3. Other Secondary Endpoints

The other secondary endpoints are as follows:

- The percent change in Reference Lesion Surface Area from Baseline to Visit 6 (Week 8).
- The proportion of subjects who achieve $\geq 60\%$ reduction in BSA of EBS lesions within the Assessment Area from Baseline to Visit 8 (Week 16)
- The proportion of subjects achieving success on the IGA of the Assessment Area, where success is defined as at least a 2-point reduction, from Baseline to Visit 8 (Week 16).

3.1.4. Exploratory Endpoints

The exploratory endpoints are as follows:

- The percent change in Reference Lesion Surface Area from Baseline to Visit 8 (Week 16).
- The proportion of subjects with a reduction in overall pain intensity from Baseline to Visit 6 (Week 8).
- The proportion of subjects with a reduction in overall pruritus intensity from Baseline to Visit 6 (Week 8).
- The proportion of subjects with a reduction in overall pain intensity from Baseline to Visit 8 (Week 16).
- The proportion of subjects with a reduction in overall pruritus intensity from Baseline to Visit 8 (Week 16).

3.2. Safety Variables

3.2.1. Adverse Events

Adverse events (AEs), which include clinical laboratory test variables, will be monitored and documented from the time of the first study medication application until the subject's study participation is complete (Week 16). Beginning with the start of the first study medication

application, investigators should make an assessment for adverse events at each visit and record the event on the appropriate AE electronic Case Report Form (eCRF). All AEs that occur after the first study medication application and up to 30 days after the subject's last study medication application will be considered treatment-emergent adverse events (TEAEs).

In concert with system-organ classification (SOC) defined by MedDRA the following AEs will be categorized as AEs of special interest (AESIs) in this study:

- All gastrointestinal (GI) disorders defined by MedDRA SOC
- Hepatic Injury
- Pancreatitis
- Urticaria/angioedema
- Epidermal necrolysis
- Drug reaction with eosinophilia and systemic symptoms (DRESS)
- Purpura/cutaneous vasculitis
- Jaundice

Each AE shall be evaluated for the severity, seriousness, duration, resolution, action taken and its relationship with the study medication.

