8.2.8. Visit 8 (Week 16/Day 113); end of the study

This visit must occur 16 weeks/112 days (± 4 days) after Visit 2.

At this visit, the investigator or designee will perform the following procedures:

1. Query the subject/caregiver in a non-directive manner about any changes in the subject's health since the previous visit and report all AEs on the appropriate form
2. Query the subject/caregiver about any changes in the subject's concomitant therapies since the previous visit and report changes on the appropriate form
3. Confirm the subject continues to comply with all study restrictions, is eligible to continue in the study and has followed all study instructions
4. Measure vital signs
5. Identify any new lesions that appeared since last visit
6. Determine BSA of EBS lesions in the Assessment Area new lesions (if new lesions exist) using the palmar method
7. Calculate the total BSA of all EBS lesions
8. Measure the LSA of the Reference Lesion
9. Perform the IGA evaluation on the Assessment Area
10. Collect blood & urine samples for clinical laboratory tests
11. Perform a urine pregnancy test for WOCBP
12. Take standardized color photographs
13. Perform ECG
14. Discharge the subject from the study.

The investigator will mark the general location of all the EBS lesions on the appropriate body chart(s) at each study visit.

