10.1. Adverse events(s)

An adverse event is defined as any untoward medical occurrence in a clinical investigation subject administered a pharmaceutical product, which does not necessarily have a causal relationship with this treatment. An adverse event can therefore be any unfavorable and/or unintended sign (including an abnormal laboratory finding), symptom, or disease temporally associated with the use of an investigational medicinal product, whether or not related to the investigational medicinal product. All adverse events, including observed or volunteered problems, complaints, or symptoms, are to be recorded on the appropriate eCRF.

Worsening of any EBS lesion assessment should be reported as an AE ONLY if the use of the study medication is interrupted or discontinued, or if therapy is required to manage the event. At each visit the Investigator should examine the lesions being treated for any adverse events specific to treatment. Events should be recorded on the appropriate eCRF.

Adverse events, which include clinical laboratory test variables, will be monitored and documented from the time of the first study medication application until the subject's study participation is complete (Visit 8/Week 16) OR until 30 days after the subject's last study medication application, whichever is longer.

Subject/caregivers should be instructed to report any adverse event that they experience to the Investigator. Beginning with the start of the first study medication application, investigators should make an assessment for adverse events at each visit and record the event on the appropriate adverse event eCRF.

Wherever possible, a specific disease or syndrome rather than individual associated signs and symptoms should be identified by the Investigator and recorded on the eCRF. However, if an observed or reported sign or symptom is not considered a component of a specific disease or syndrome by the Investigator, it should be recorded as a separate adverse event on the eCRF. Additionally, the condition that led to a medical or surgical procedure (*e.g.*, surgery, endoscopy, tooth extraction, or transfusion) should be recorded as an adverse event, not the procedure.

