8.2. Adverse Events

Adverse events will be coded using the Medical Dictionary for Regulatory Activities (MedDRA) version 19.0 and summarized by treatment group, system organ class, and preferred term.

A summary overview of TEAEs will be provided which presents the number and percentage of patients in each treatment group satisfying each of the following categories:

- All TEAEs,
- Drug-related TEAEs,
- Maximum severity of TEAEs,
- Maximum severity of drug-related TEAEs,
- All AESIs,
- Drug-related AESIs,
- Maximum severity of AESIs,
- All treatment-emergent SAEs,
- Drug-related treatment-emergent SAEs,
- Death due to TEAEs,
- TEAEs leading to study drug discontinuation, and
- Drug-related TEAEs leading to study drug discontinuation.

The numbers and percentages of patients with TEAEs will be summarized by MedDRA preferred term within system organ class, by treatment group and overall. For the summaries by treatment group, multiple AEs with the same MedDRA preferred term within system organ class from the same patient within a given treatment will only be counted once. For overall summaries, multiple AEs with the same MedDRA preferred term within system organ class from the same patient will only be counted once.

All TEAEs related to study drug, AESIs, SAEs, and AEs leading to study drug discontinuation will be summarized in the same manner. Summaries will also be provided for the numbers and

percentages of patients by system organ class, preferred term, and maximum severity, for TEAEs, AESIs, and drug-related TEAEs.

All AEs will be included in by-patient listings containing additional information of interest such as onset and resolution times, maximum severity, causal relationship to study medication, and action taken. Specific by-patient listings of AESI, SAEs, and TEAEs leading to study discontinuation will be provided.

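### The SAP's 30-day limit on treatment-emergent events leaves about the last 27 days of follow-up out of the main adverse event tables; this is narrower than the protocol and is not declared as a change

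*SAP*

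**What the plan says.** SAP 3.2.1 sets the definition: events after the first application and "up to 30 days after the subject's last study medication application will be considered treatment-emergent adverse events (TEAEs"). SAP 8.2 then builds its main displays on that term: "A summary overview of TEAEs will be provided", followed by incidence by system organ class (SOC) and preferred term (PT), drug-related TEAEs, and maximum severity.

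The protocol is wider in two places. Section 10.1 follows AEs "until the subject's study participation is complete (Visit 8/Week 16) OR until 30 days after the subject's last study medication application, whichever is longer". Section 11.2.4 commits to a summary with no cut-off after the last dose: "New or worsening adverse events after dosing of study drug will be summarized by system organ class, preferred term, and treatment".

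SAP section 12 (Table 2) lists the changes from the protocol. Its row on adverse events covers only the list of events of special interest (AESIs). The 30-day limit is not mentioned.

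**The concern.** The eight-week no-treatment follow-up is part of the design, and the SAP still compares BSA and IGA success between arms at Week 16. The main AE comparison stops earlier, at a point that the protocol does not set.

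Two features make the gap more than cosmetic. First, Protocol 9.2.4 schedules laboratory samples at Visits 1, 2, 4, 6 and 8, so Visit 8 is the only scheduled draw after treatment ends. A clinically relevant abnormal result there is reportable as an AE. If its onset is dated to that visit, it falls outside the window. Second, the window is tied to each subject's last application. A subject who stops treatment early but stays in follow-up has a shorter TEAE window than one who completes treatment. If early stopping differed by arm, the TEAE tables would compare the arms over different lengths of time.

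**Working it through.** **Inputs**

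- Window end = day of last application + 30 (SAP 3.2.1), with Day 1 the day of first treatment (SAP 5.2).
- Treatment ends at Visit 6: "Visit 6 (Week 8/Day 57) end of the treatment period". The visit may move by 4 days either way (Protocol 8.2.6), so Days 53-61.
- Applications are in the evening (SAP 2.2) and the tubes are taken back at Visit 6 (Protocol 8.8.5). I therefore place the last application on the evening before Visit 6, and also show the result if it falls on the day of Visit 6.
- Visit 8 is Day 113, again with 4 days either way (Protocol 8.2.8), so Days 109-117.

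**Check of the calendar.** 42 days of screening + 112 days from Visit 2 to Visit 8 + 4 days of window = 158, which matches the maximum duration in Protocol 8.7.

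**Days outside the TEAE window** = Visit 8 day - (last application day + 30)

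| Case | Last application | Window ends | Visit 8 | Days outside |
|---|---|---|---|---|
| On schedule | 56 | 86 | 113 | 27 |
| On schedule, last application on day of Visit 6 | 57 | 87 | 113 | 26 |
| Longest gap (Visit 6 early, Visit 8 late) | 52 | 82 | 117 | 35 |
| Shortest gap (Visit 6 late, Visit 8 early, last application on day of Visit 6) | 61 | 91 | 109 | 18 |

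On schedule, 27 days is 27/113 = 24% of study days and 27/(113 - 56) = 27/57 = 47% of the days after the last application. In every permitted combination, Visit 8 is at least 18 days past the window.

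**Early stoppers who stay on the visit schedule.** Days outside = 113 - (d + 30) = 83 - d, where d is the day of the last application. This gives 40 days for d = 43, 54 for d = 29, 69 for d = 14 and 75 for d = 8.

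**Which displays are affected (SAP 8.2)**

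- Tied to TEAEs: the overview rows for all and drug-related TEAEs, their maximum severity, deaths and discontinuations; the overview SAE rows, which are labelled treatment-emergent; the SOC/PT incidence table; the tables of drug-related TEAEs; and the SOC/PT tables by severity for both.
- No window stated: the opening sentence of 8.2, which promises AEs by treatment group, SOC and PT; the AESI rows and tables; and the later sentence that summarises SAEs and AEs leading to discontinuation of study drug.
- Not limited: the by-patient listings of all AEs, and the by-arm, by-visit summaries of laboratory values, vital signs and ECGs (SAP 8.3 to 8.5).

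The second group is where the ambiguity lies. The text allows either an all-AE table by arm or none.

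**The case against.** A 30-day window is a defensible choice. The protocol uses the term TEAE in section 3.2 without defining it, and section 11.2 leaves analysis detail to the SAP. The opening sentence of SAP 8.2 has no TEAE limit and resembles Protocol 11.2.4, and SAP section 8 rests safety on new or worsening events, also with no cut-off. All of this stands. It means that the fault is a narrowing that is neither declared nor clearly backed by another table. The choice of 30 days is not an error in itself.

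A reader might infer more than the documents support:

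- *That late events appear only in listings.* The SAP does not say so. The opening sentence of 8.2 and the AESI rows may capture them.
- *That hepatic injury or pancreatitis first seen at Visit 8 drops out.* Both are AESIs, the AESI tables state no window, and Protocol 10.4.3 requires a narrative for every AESI.
- *That nothing first found at Visit 8 can be a TEAE.* Visit 8 does include the step "Collect blood & urine samples for clinical laboratory tests" and an ECG, but TEAE status follows onset, not detection. An event dated back into the window counts, and SAP 5.4 treats a missing start date as treatment-emergent unless the partial date rules that out.
- *That the SAP shortens AE collection.* SAP 3.2.1 describes monitoring "until the subject's study participation is complete (Week 16") and omits the protocol's clause "OR until 30 days after the subject's last study medication application, whichever is longer". But sites collect under the protocol, and for a subject who leaves early the TEAE rule already reaches 30 days after the last application. This has almost no effect on the analysis.

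The early-stopper argument is also conditional. The documents give no figure for intolerance by arm. Protocol 7.7 keeps subjects who stop treatment on the visit schedule, whereas 8.8.8 removes some of them from the study. Those passages need to be reconciled, and until then it is unclear how many such subjects would stay in follow-up.

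**Conclusion.** The point holds as one of scope and declaration. The SAP's TEAE tables omit AEs with onset in the last 27 days for an on-schedule subject. The omitted period is 18-35 days across the permitted visit timings and longer for anyone who stops early and stays in follow-up. Protocol 11.2.4 has no such limit, Table 2 does not record the narrowing, and SAP 8.2 does not settle whether another by-arm AE table fills the gap.

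The result rests on evening dosing that ends at about Visit 6 and on onset dates that are complete and fall after the window. The size is in days. The documents give no expected rate of late events, so the number of events affected cannot be estimated. The consequence is an incomplete comparison of AE incidence between arms, not a loss of safety data.

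**What to change.** Make one of two changes in SAP 3.2.1 and 8.2:

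1. Extend the TEAE definition through Visit 8 or 30 days after the last application, whichever is longer. This matches Protocol 10.1 and 11.2.4. For an on-schedule subject the excluded days fall from 27 to 0.
2. Keep the 30-day TEAE tables and add a by-arm SOC/PT table of all new or worsening AEs from the first application through Visit 8.

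In either case, state which window the AESI and SAE tables use, and add a row to SAP Table 2 against Protocol 11.2.4. SAP section 1 allows revisions before database lock.

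The cost is a few sentences and one extra table set, from data already collected. The downside is slightly higher counts that include events remote from dosing. The second option limits this by showing the two periods separately.
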